6.2 Baseline Assessments (up to 30 days prior to procedure)

The following information will be assessed and documentation will be maintained as source records at the study site:

- Neurological assessment of the subject and evaluation of symptoms will be performed by an experienced neurosurgeon, neurointerventionalist or authorized designee. In the case of a ruptured aneurysm, the severity of symptoms is to be administered and assessed by authorized and certified research staff using both the National Institutes of Health Stroke Scale (NIHSS) and the Hunt and Hess scale (Table 3)..
- The Subject's modified Rankin Scale (mRS) assessment score will also be collected for the eCRF to reflect baseline functional status
- SF-36 questionnaire to assess general quality of life (for ruptured cases when the subject is impaired and unable to complete the SF-36 questionnaire, this can be completed by the subject prior to discharge)
- Medical History
- Current medications history including anti-platelet and anti-coagulation drugs
- Physical Examination
- Laboratory values to include hemoglobin (Hg), platelet count (Plt), prothrombin time (PT), partial thromboplastin time (PTT), international normalized ratio (INR), and creatinine (Cr). A pregnancy test is required if the subject is female with child-bearing potential. Any female of child-bearing potential who has not been diagnosed with menopause or any other clinical condition that would prohibit conception and/or has not undergone any kind of surgery that would prohibit conception (e.g. total hysterectomy or bilateral oophorectomy) should receive a pregnancy test prior to enrollment.
- A CT scan or MRI may be used to evaluate study Subject eligibility. However, this imaging is not required to be recorded on the eCRF nor is the imaging CD required to be sent to the Imaging Core Lab or Sponsor.

Once the consent form has been signed, all subjects should complete the baseline assessments discussed in Section 7.2 and the Schedule of Assessments (Table 4).

6.2.1 Clinical and radiographic evaluation

A pre-treatment clinical assessment will be performed by the treating physician or designee and a mRS score should be obtained. The NIHSS and Hunt and Hess scale scores will be recorded for those patients presenting with ruptured aneurysms and/or SAH. The patient's medical co-morbidities will also be recorded for study analysis. Results of a pre-embolization brain angiography, MRA or CTA may be recorded and submitted to the Imaging Core Lab and Sponsor if imaging was performed within 30 days prior to enrollment (optional). Measurement of the three (3) aneurysm dimensions of interest (height, length, and width), its neck size and maximal diameter will be recorded as well as any additional relevant radiographic features (e.g. partial thrombosis, peri-aneurysmal edema, etc.).

For conventional angiography, two 10 mm silicon-coated spherical ball bearings must be used for each enrolled subject during procedural angiography (immediately pre- and post-coiling) as well as during any subsequent follow-up angiograms to make measurements as standardized as possible. One ball bearing will be placed on the forehead and the second in the periauricular area ipsilateral to the aneurysm. Image intensifiers will be placed as close to the head as possible. A 4-axis orthogonal view of the aneurysm will be obtained.

Imaging data will be recorded on the Imaging eCRF. Imaging CDs will be sent to the Imaging Core Lab and the Sponsor, Northwestern University. In the event ball bearings are not used during procedural angiography, the Sponsor may require submission of baseline imaging including CTA or MRA to enable the Imaging Core Lab to more accurately obtain measurements.

Please see Table 7 which outlines the imaging schedule.

6.3 Randomization

Subjects who meet study inclusion and exclusion criteria and who have signed an informed consent form will be randomized through the study's Electronic Data Capture (EDC). Randomization will be performed through the EDC on the day of the coiling procedure. This must be completed once pre-coiling imaging has been reviewed and immediately before endovascular coiling begins. At this time, the Subject will be given a unique study identification number generated by the EDC. This number should be used on all study documents so that data is reported anonymously to protect subject confidentiality and patient health information (PHI). Patients will be randomized 1:1 to one of two study arms: 1) The HydroCoil® Embolic System ("Hydrogel Group") or 2) bare platinum coils ("Platinum Group").

Patient safety is a priority. In the event the treating investigator deems it clinically necessary to switch a subject randomized to the Hydrogel arm to the platinum coils arm for safety reasons, the crossover should be documented as a protocol deviation in the eCRF. However, the subject will continue to be followed and will receive all study-related procedures as per protocol. Similarly, if the investigator switches a subject, randomized to the bare platinum arm to the Hydrogel arm or uses more than 10% platinum coils (based on length) in a subject randomized to the Hydrogel arm, the same procedures will be followed. The reason(s) for the preference of one type of coils over the other will be documented in the eCRF.

If during the course of the treatment the investigator decides to perform staged coiling or to use a flow-diverting stent (e.g. pipeline), a protocol deviation should be documented in the eCRF and the subject should continue to be followed as per protocol.

If during the course of the treatment the investigator decides to switch to open surgery or decides not to treat the aneurysm at all, a protocol deviation should be documented and subjects should continue to be followed according to standard of care (i.e. as per site management protocol). The reason for the preference of surgery or no treatment over coiling will be documented on the eCRF.

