4.3 Secondary Outcomes

- Packing density as measured by the volumetric filling of the aneurysm
- Rate of initial complete occlusion
- Procedure and/or device-related morbidity and mortality
- Clinical outcome at 18 to 24 months as assessed using the modified Rankin Scale
- Re-treatment rates
- Hemorrhage from target aneurysm during follow-up
- Aneurysm occlusion stability
- Major versus minor recurrence

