5.2 Study Duration and Enrollment

The duration of the open enrollment phase will be 24 months or until the required number of patients are enrolled. Each patient will have a post-procedure follow-up of at least 18 months.

The number of Subjects to be enrolled, and randomized, in the study is up to 600. This sample size calculated to provide sufficient statistical power to show the anticipated difference in initial occlusion and recurrence rates between the 2 study arms (see section 9 for detailed statistical analysis). Patients will be recruited from up to 50 national and international centers. Each Investigational Site will be expected to enroll at least 20 Subjects. Each site must meet the eligibility criteria.

A multidisciplinary approach is expected from each qualified study center. The Neurovascular teams should include the appropriate specialties for the proper conduct of the study e.g., neurointerventionalist(s), experienced in intracranial aneurysm coiling, neurosurgeon(s), and study coordinator(s). In addition, the treating physician must meet a minimal level of expertise consisting of at least 5 successful intracranial aneurysm coiling procedures utilizing the HydroCoil Embolic system prior to enrolling patients into the study.

Each site must provide written approval from their reviewing Institutional Review Board (IRB) and all other required regulatory documentation prior to consenting and enrolling the first Subject.

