6.1 Screening and Consent

Eligibility will be assessed once the neurovascular team makes a decision on endovascular treatment of an aneurysm. A local site log of all eligible patients will be kept and a copy returned to the coordinating site (Northwestern University) when requested by the study monitor.

If a patient fulfills the inclusion and exclusion criteria, an authorized member of the research team will discuss the trial and provide the patient or his/her LAR with the informed consent form. The patient or LAR will be provided adequate time to consider participation in the trial and the research team will answer all questions regarding the trial. A copy of the consent will be retained in the patient's medical record, one will be given to the patient, and the original will be retained by the local site.

All patients who meet the eligibility criteria and give written informed consent are eligible for enrollment into the study which occurs at the time of randomization

Screen failures are defined as a subject consented and screened for enrollment, but not ultimately enrolled on the day of randomization; provided that the failure to enroll was attributable to the subject's failure to meet the inclusion or exclusion criteria listed in the protocol.

Screen failures and subjects who electively withdraw from the study will be dropped from any further follow-up and statistical analysis of this study. The original ICF and any data collected up until the date of withdrawal will be maintained in the clinical site's study files and their number will not be used again in the study.

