8.2 IRB Approval

The Investigator or the study coordinator is responsible for submitting the study protocol and any changes issued by the Sponsor during the course of the study for IRB approval prior to any Subject enrollment and amendments taking effect as well as obtain renewals at periods determined by the IRB for the duration of the study.

9 Statistical Methods

Primary analysis of primary and secondary outcomes will be based on the intent-to-treat (ITT) principle. Secondary analyses will examine differences based on per protocol principles, as well as a detailed analysis of missing data, should there be any (see below).

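### Randomized subjects switched to open surgery or left untreated come off the protocol visit schedule, so their 18 to 24 month mRS and scheduled adverse event review are not assured in an analysis declared ITT

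*Combined protocol and SAP*

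**What the plan says.** Section 6.3 sets two follow-up tracks after randomization.

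- **Protocol track.** For a crossover between coil types, or platinum above the 10% limit in the Hydrogel arm, "the subject will continue to be followed and will receive all study-related procedures as per protocol". For staged coiling or a flow diverter, "a protocol deviation should be documented in the eCRF and the subject should continue to be followed as per protocol". Section 6.6.1 likewise keeps subjects given disallowed coils or liquid embolics on trial follow-up.
- **Site track.** "If during the course of the treatment the investigator decides to switch to open surgery or decides not to treat the aneurysm at all", the deviation and its reason are recorded, and "subjects should continue to be followed according to standard of care (i.e. as per site management protocol".

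Section 6.1 says that eligible, consenting patients "are eligible for enrollment into the study which occurs at the time of randomization", and section 6.3 places randomization on the day of the procedure, immediately before coiling starts. Section 9 opens: "Primary analysis of primary and secondary outcomes will be based on the intent-to-treat (ITT) principle". Section 4.3 lists among the secondary outcomes "Clinical outcome at 18 to 24 months as assessed using the modified Rankin Scale", together with procedure- or device-related morbidity and mortality, and hemorrhage from the target aneurysm. Section 5.2 adds: "Each patient will have a post-procedure follow-up of at least 18 months".

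**The concern.** The decision to operate, or not to treat, is taken after allocation by an operator who knows which coils were assigned. The subjects concerned are in the ITT set, but theirs is the only treatment deviation in section 6.3 that loses the visit schedule. The Raymond scale may mean little for an aneurysm that was never coiled. The mRS, survival, hemorrhage and adverse events remain fully defined after surgery or no treatment.

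If the 18 to 24 month mRS is then absent for a reason tied to how the subject fared, the clinical comparison no longer covers everyone randomized, and the remaining subjects are a selected group. Section 9 does not repair this. Section 9.2.1 leaves the missing-data method until the patterns have been seen, and section 9.2.2 relies on an available-data mixed model, which does not remove bias when missingness depends on the unobserved outcome.

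**Working it through.** **1. What each track requires**

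| Item | Coil crossover, staged coiling, flow diverter | Open surgery or no treatment |
|---|---|---|
| In the ITT set (6.1, 9) | Yes | Yes |
| mRS at 3–12 and 18–24 months (6.9, 6.10, Table 4) | Required | Not required; depends on site practice |
| SF-36 at the same visits | Required | Not required |
| Scheduled adverse event review (6.8 to 6.10) | Required | Not required |
| AE/SAE reporting (7.1, 7.2) | Required | Required; no exception stated |
| Death forms within 24 hours (6.13) | Required | Required; no exception stated |
| Rule in section 9 for these subjects | General missing-data text only | General missing-data text only |

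The gap is therefore in scheduled assessment, chiefly the late mRS. Event reporting remains in force, but without the visits that would prompt it.

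**2. Primary endpoint.** Sections 4.2 and 6.4 define recurrence as progression on the Raymond scale. An aneurysm never coiled has no evident post-coiling grade to progress from, and no text says how the ITT analysis counts it.

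**3. The plan's own power figure.** Inputs from section 9.1 and Table 5: 300 per arm, 33.0% against 22.8%, two-sided 5%. With the pooled-variance normal approximation without continuity correction,

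power = Φ{ [|p1 − p2|·√n − 1.96·√(2·p̄·(1 − p̄))] / √(p1(1 − p1) + p2(1 − p2)) }, with p̄ = 0.279.

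- n = 300: [0.102 × 17.321 − 1.96 × 0.6343] / 0.6302 = 0.831, so power is 79.7%. The required total is 606. Both agree with the stated 80% and 600.
- n = 297 (1% of each arm not evaluable): 79.3%.
- n = 291 (3% of each arm not evaluable): 78.5%.

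Loss of power is not the issue.

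**4. How far missing outcomes could move a risk difference.** The documents give no rate of conversion to surgery or no treatment, so 1% to 3% per arm is an assumption. Let d be the difference among observed subjects and f the fraction missing in each arm. Setting all missing subjects to the event in one arm and to no event in the other gives

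bounds = (1 − f)·d ± f.

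- Binary mRS outcome with d = 0: ±1 point at f = 1% and ±3 points at f = 3%. This does not depend on the event rate.
- Unequal loss, 3% Hydrogel and 1% Platinum, with an assumed 10% event rate in both arms. Upper bound: (29.1 + 9)/300 − 29.7/300 = +2.8 points. Lower bound: 29.1/300 − (29.7 + 3)/300 = −1.2 points.
- Recurrence with the plan's d = −10.2 points. At f = 1%: −10.1 ± 1, that is −11.1 to −9.1. At f = 3%: −9.9 ± 3, that is −12.9 to −6.9.

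**The case against.** The strongest reply is that these subjects are not abandoned. Section 6.3 says that follow-up continues, and conversion is not among the withdrawal reasons listed in section 6.13 (a list stated to be non-exhaustive). The 18-month statement in section 5.2 is not plainly broken either, since site follow-up has no stated end. Section 6.11 asks for an mRS at an unscheduled visit when neurological status changes because of an adverse event, so some deteriorations would be recorded. All of this stands. For the mRS, the right description is not required on schedule; some sites may well record it.

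A reader might infer that deaths and adverse events are missing by design. The documents do not support that. The death rule in section 6.13 and the AE/SAE rules in sections 7.1 and 7.2 make no exception for subjects not coiled.

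A reader might also infer that the loss falls mainly in one arm and flatters the arm with more procedural failures. That too is unsupported. Subjects in whom only the assigned coil type failed, and who received the other type, stay on the protocol track. Nothing in the documents ties surgery or non-treatment to coil type, and a decision not to treat need not follow a complication. If these subjects do better than average, the bias runs the other way. Nor can a share of poor outcomes lost be calculated: the conversion rate, the outcome in this group and the overall rate of poor outcome would all have to be assumed.

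What remains is that the 18 to 24 month mRS is not assured for part of the ITT population, and that no analysis rule covers these subjects.

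**Conclusion.** The point holds in limited form. Section 6.3 takes one class of randomized subjects off the visit schedule while section 9 keeps them in the ITT analysis without saying how. Late mRS, SF-36 and scheduled adverse event review are not assured for them; deaths and reportable events are exposed only to less complete ascertainment.

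On an assumed 1% to 3% of each arm without an mRS, the extreme-case bounds on the risk difference are about ±1 to ±3 percentage points around an observed null. The direction is unknown. These are limits, not an expected bias, and they assume that no site records the outcome. For recurrence, the same fractions leave the planned difference clearly in favor of Hydrogel and cost about one point of power. This is an inexpensive improvement worth making, not a defect that undermines the trial.

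**What to change.** **Section 6.3.** Amend it so that all randomized subjects, including those not coiled, stay on the protocol schedule to 18 to 24 months for non-imaging outcome data: mRS, adverse event review, target-aneurysm hemorrhage and vital status. Add the SF-36 if the quality-of-life comparison is also to cover all randomized subjects. Section 6.8 allows telephone contact only for the 3 to 28 day visit, where that visit is not standard of care. The amendment has to extend that option explicitly to the later visits for these subjects. No imaging is added, and patient care stays with the site.

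**Section 9.** State that subjects never coiled have no baseline Raymond grade. Report their number and the reasons by arm. Add a sensitivity analysis of the primary endpoint that includes them under stated assumptions, for example counted once as recurrence and once as no recurrence, and with the two assumptions crossed between arms to give the bounds. Neither assumption matches the endpoint definition exactly, so these analyses should be presented as bounds on the primary result.

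**Cost.** Protocol wording, one analysis rule and a few extra visits or calls.

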6.4 Angiographic occlusion evaluation

Angiographic aneurysm occlusion rate will be assessed using 2 scales. The first is based on the new reporting standards described by Meyers et al. (grades 0 to 5).²³ This reporting system will be used by the Imaging Core Lab only for study and validation purposes. It is comprised of 6 grades: (Figure 1)

- Grade 0: complete and total aneurysm occlusion
- Grade 1: \geq 90% volumetric aneurysm occlusion
- Grade 2: 70% to 89% volumetric aneurysm occlusion
- Grade 3: 50% to 69% volumetric aneurysm occlusion
- Grade 4: 25% to 49% volumetric aneurysm occlusion
- Grade 5: < 25% volumetric aneurysm occlusion

The second scale will be the Raymond scale²⁴ (complete, residual neck and residual aneurysm) (figure 2). This scale will be used by the Imaging Core Lab and the investigator at each participating site to report aneurysmal occlusion rates.

In the event of recanalization*, the treating physician will be asked to grade the recurrence by answering the following questions:

- 1- Can the aneurysm be retreated? YES or NO
- 2- Should the aneurysm be retreated? YES or NO
- 3- If answers to both questions are YES, the treating physician will be asked to indicate the most appropriate subsequent treatment option (i.e. recoiling, clipping, stent-coil, flow diverter stent, or parent artery occlusion).

*As part of the Imaging Core Lab's evaluation of the submitted imaging, they will also perform the above assessments for study purposes, but will do so while being blinded to the treating physician's grading and assessment. The Imaging Core Lab will be unblinded to the rupture/unruptured status of the aneurysm as this may affect their decision making process in case retreatment is warranted.

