4.4 Safety Outcomes

- Peri-aneurysmal edema
- Aseptic meningitis
- Thromboembolic events
- Vasospasm
- Ventricular Enlargement
- Hydrocephalus
- Aneurysm Rupture
- Parent Vessel Occlusion

5 Clinical Study Design

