6.6 Treatment protocol

6.6.1 Coiling procedure

Coiling will be performed according to the standards of each institution. The choice of catheters and guide-wires will not be dictated. The investigator will also have the choice to use assist devices (balloon and/or stents). The use of assist devices will be recorded on the Procedure eCRF. No flow diverter stents are to be utilized in this study. Coiling will be done in a one-step procedure. Every attempt should be made to treat with as much of the randomized coil type as possible to achieve optimal occlusion. Use of any bioactive or non-HES 2nd generation coils (e.g. Matrix, EV3 or Cerecyte) and/or use of liquid embolic materials is not allowed. Use of such devices will be considered a protocol deviation but the subject will continue to be followed according to HEAT protocol.

The use of Antiplatelet therapy is left to the discretion of the treating physician. Antiplatelet therapy type and dosing should be recorded on the eCRF. Timing of anticoagulation and ACT during the procedure should be documented on the eCRF.

For the Platinum group, any type of FDA or HPB approved or cleared (as applicable) bare platinum coils can be used. For the Hydrogel group, the investigator will use any type of FDA or HPB approved or cleared (as applicable) second generation HydroCoil Embolic System product (which includes HydroSoft, HydroFrame, HydroFill and future FDA or HPB approved hydrogel products). For subjects randomized to the Platinum arm, treatment should involve exclusive use of bare platinum coils. For subjects randomized to the Hydrogel arm, treatment should involve exclusive use of HES products with up to 10% of total coil length using bare platinum allowed.

After the procedure, digital copies of the pre and post-coiling angiograms with AP and lateral working projections will be sent to the Imaging Core Lab for independent evaluation and analysis. A copy will also be sent to the Sponsor, Northwestern University. The images will be de-identified and the CD/DVD will be labeled with the subject's assigned study identification number, imaging type, and date of imaging.

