7.1 Definitions

An Adverse Event (AE) is any undesirable clinical event occurring to a subject enrolled in the trial, whether or not it is considered related to the investigational product. This includes a change in a patient's clinical condition including changes in neurological status or laboratory results that has or could have a deleterious effect on the patient's health or well-being.

An Adverse Device Effect (ADE) is any AE related to the deployment of any coil type.

A Serious Adverse Event (SAE) or a Serious Adverse Device Effect (SADE) is an event that:

- Results in death
- Is life threatening
- Is disabling
- Requires initial or prolonged hospitalization (does not include planned hospitalization)
- Requires intervention to prevent permanent impairment / damage

An Unanticipated Adverse Device Effect (UADE) is any serious adverse effect on health or safety or any life threatening problem or death caused by, or associated with, a device, if that effect, problem or death was not previously identified in nature, severity or degree of incidence in the investigational plan, or any other unanticipated serious problem associated with a device that relates to the rights, safety, or welfare of subjects.

See Figure 3 for a classification of adverse events.

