7.2 Reporting of Adverse Events

For this post-market study, only AE/SAEs that are related to the procedure, device or a change in neurological status should be captured on eCRFs and in the Subject's medical records, for both treatment arms. In case of occurrence of any SAE and/or UADE, the site's principal investigator shall promptly submit a report along with any other required documentation to the Sponsor, Northwestern University and funder, MicroVention, Inc and follow site-specific IRB procedures.

If there is a serious adverse event, the clinical study site will report such to the Sponsor, Northwestern University and the funder, MicroVention, Inc within 24 hours of learning the event.

If there is an unanticipated adverse device effect, the Principal Investigator will submit a report to the Sponsor, Northwestern University and the funder, MicroVention, Inc and to the reviewing IRB as soon as possible, but not later than 10 working days after the investigator learns of the effect.

All other reportable events should be reported no later than 10 working days after the investigator or site first become aware of the adverse event in question.

The adverse event report should at least include the following parameters:

- Date of event and time
- Type of event (E.g., AE, SAE, UADE)
- Narrative
- Duration of adverse event or adverse device effects (start-end)
- Treatment
- Outcome/Resolution Status

The principal investigator and the principal investigator of the site shall present any additional information or documentation (e.g. imaging results) to the DSMB and steering committee if required by these committees.

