7.3 Expected Risks

Known risks associated with aneurysm coiling are as follows:

- Aseptic meningitis
- Inflammation
- Thromboembolic events
- Stroke
- Vasospasm
- Hydrocephalus
- Aneurysm Rupture
- Coil protrusion into parent vessel
- Parent Vessel Occlusion
- Premature coil detachment (coil breakage due to technical device malfunction)
- Death

8 Ethics and Regulatory Considerations

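### Parent vessel occlusion is a listed safety outcome with no definition and no blinded core-lab read assigned, so its ascertainment rests on reports from sites that know the coil type

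*Combined protocol and SAP*

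**What the plan says.** Section 4.4 names "Parent Vessel Occlusion" among the safety outcomes, without a definition, assessor, time point or symptom requirement. Section 7.3 lists it again among the known risks of coiling, next to "Coil protrusion into parent vessel".

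Images reach a reader who does not know the arm. Section 6.6.1 says the pre- and post-coiling angiograms "will be sent to the Imaging Core Lab for independent evaluation and analysis". Section 6.2.1 adds that "Imaging CDs will be sent to the Imaging Core Lab and the Sponsor, Northwestern University". Sections 6.9 and 6.10 schedule an angiogram at 3 to 12 and at 18 to 24 months, and allow MRA instead where that is local practice. Section 6.5 states that the core lab is blinded to coil type.

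The core lab's named tasks are in 6.4 and 6.5: the six-grade volumetric occlusion scale, the Raymond scale ("This scale will be used by the Imaging Core Lab and the investigator at each participating site to report aneurysmal occlusion rates"), the retreatment questions and the aneurysm volume. Parent artery occlusion appears in 6.4 only as a possible retreatment, not as a finding to record.

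Adverse events follow another route. Section 7.1 says "An Adverse Event (AE) is any undesirable clinical event occurring to a subject enrolled in the trial", and goes on to include changes in condition that could harm the patient. Section 7.2 then limits recording: "only AE/SAEs that are related to the procedure, device or a change in neurological status should be captured on eCRFs". Under 12.1 the DSMB evaluates reported serious events and device effects for their relationship to device or procedure.

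**The concern.** The protocol arranges blinded reading for its efficacy outcomes but assigns none to a safety outcome that the same angiograms can be expected to show. The treating team knows the coil type because it implants the coils, and no blinded site assessor is described. Whether an asymptomatic occlusion enters the database depends on the site noticing it, regarding it as an adverse event and judging it related.

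This matters because the study hypothesis (4.1) is that hydrogel packs the aneurysm more densely, with coils that swell after placement (3.3). Compromise of the adjacent vessel is a plausible harm on which to compare the arms. Incomplete reporting at the same rate in both arms costs precision. Reporting that differs by arm biases the comparison, and the bias could run either way.

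**Working it through.** **Step 1. Trace the outcome through the protocol.**

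| Question | What the protocol provides |
|---|---|
| Is it an outcome? | Yes (4.4); also a known risk (7.3) |
| Is it defined? | No |
| Who holds the images? | Site, sponsor and core lab (6.2.1, 6.6.1) |
| Who is blinded to coil type? | The core lab (6.5) |
| What is the core lab told to read? | Two aneurysm occlusion scales, retreatment questions, aneurysm volume (6.4, 6.5) |
| Is a parent-vessel read assigned? | None found |
| How does it reach the database? | Site adverse-event report (7.1, 7.2) |
| Is there independent review? | DSMB, for events already reported (12.1) |

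The open entry in 6.2.1 for further radiographic features belongs to the pre-treatment evaluation. It names neither a reader nor the parent vessel.

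**Step 2. Reproduce the plan's own figure.** The plan gives no figure for this outcome, so Table 5 recurrence serves to check the formula. With n per arm and p̄ the mean of the two rates:

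power = Φ{ [ |p1 − p2| − 1.96 √(2p̄(1−p̄)/n) ] / √( p1(1−p1)/n + p2(1−p2)/n ) }

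Inputs from 9.1 and Table 5: n = 600/2 = 300, p1 = 0.330, p2 = 0.228, p̄ = 0.279. This gives Φ[(0.102 − 1.96 × 0.0366)/0.0364] = Φ(0.83) = 0.797, which matches the stated 80%.

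**Step 3. Under-reporting, equal in both arms.** The rates are assumed; n = 300 per arm.

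- True 6% v 2% (18 v 6 expected events), all reported: Φ[(0.04 − 1.96 × 0.0160)/0.0159] = Φ(0.54) = 0.71. Exact Fisher power is 0.66.
- Half reported, so 3% v 1% (9 v 3 events): Φ[(0.02 − 1.96 × 0.01143)/0.01140] = Φ(−0.21) = 0.42. Fisher 0.31.
- Three quarters reported (13.5 v 4.5 events): 0.58 by the same formula.
- Lower true rates of 3% v 1%: 0.42, 0.33 and 0.23 when all, three quarters or half are reported.

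**Step 4. Reporting that differs by arm, with equal true rates.** Observed rate = true rate × share reported. The chance of a two-sided p below 0.05 was found by enumerating the binomial counts.

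| True rate, both arms | Share reported | Observed rates | Chi-square | Fisher |
|---|---|---|---|---|
| 4% | 80% v 60% | 3.2% v 2.4% | 9% | 6% |
| 4% | 80% v 40% | 3.2% v 1.6% | 25% | 17% |
| 2% | 80% v 40% | 1.6% v 0.8% | 13% | 6% |

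The expected risk ratio is 0.80/0.60 = 1.33 or 0.80/0.40 = 2.0 where the truth is 1.0. With counts this small the normal approximation in Step 3 is rough, which is why Fisher values are given for the main cases.

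**The case against.** A reader might infer that the core lab looks at nothing but the aneurysm. The documents do not say so. Section 6.6.1 sends it the procedural images without limiting the evaluation, section 6.4 is about aneurysm occlusion and need not describe the whole remit, and neither a core-lab charter nor the Imaging eCRF is included. What the text supports is narrower: the protocol itself assigns no parent-vessel read. If a charter already contains one, a cross-reference would supply most of the fix, but 4.4 would still lack a definition and a data source.

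A reader might also infer that silent occlusions are lost. That does not follow. The filter in 7.2 has alternatives, and an event related to the procedure or device qualifies without any neurological change. The definition in 7.1 extends to changes that could be harmful, sites see the same scheduled images, and 7.3 alerts them to this risk. A silent occlusion that the site sees and judges related can be reported. What remains is that this depends on an unblinded judgement, with no patency field specified to prompt it.

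The DSMB adds independent review of relationship, but nothing asks it to look for unreported events.

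The power figures carry limited weight. The trial is sized on efficacy outcomes, 9.2 specifies no test for the 4.4 list by name, and every rate in Steps 3 and 4 is assumed. With a modest reporting gap, false significance is close to nominal. These points limit the size of the concern but leave the gap in ascertainment in place.

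**Conclusion.** The concern holds in this form: a named safety outcome has no definition and no assigned blinded read, and as written it depends on adverse-event reports from sites that know the arm. Asymptomatic occlusions can be missed or reported unevenly.

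The size cannot be derived from the documents. Under the assumed rates, halving the reporting takes power at 6% v 2% from 0.71 to 0.42 (Fisher 0.66 to 0.31). At equal true rates of 4%, false significance ranges from about 9% (Fisher 6%) to 25% (Fisher 17%), depending on the reporting gap. The direction is firmer than the size: incomplete capture reduces power, and capture that differs by arm biases the comparison. The conclusion also assumes that the vessel can be judged on the submitted images, which is reasonable for angiography and less certain for MRA. The primary endpoint is unaffected.

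**What to change.** Define parent vessel occlusion in 4.4. Add one field to the blinded core-lab form, parent vessel patent / narrowed / occluded, completed for the post-coil angiogram and for each submitted follow-up image. State in 4.4 that the arms are compared on this blinded reading whether or not the occlusion caused symptoms, and show site-reported events separately. Fields for branch occlusion and coil protrusion are optional, since 4.4 names neither as an outcome.

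The cost is small: extra form entries, using the existing reader and images, with no new visit. Counts will rise in both arms because silent findings are included. Readings will be less reliable where follow-up is by MRA, so report follow-up results by imaging modality; the required post-coil angiogram does not have that limitation.
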